8.3. Overall Survival (OS)

The OS analysis will be based on ITT set and will include all OS data, including data after crossover.

Overall survival is defined as the time in months from the randomization date to the date of death due to any cause. Subjects without documentation of death at the time of the data cutoff for analysis will be censored at the date the subject was last known to be alive, or the data cutoff date, whichever is earlier. The last known alive date is the last record in the study database. For example, this date may be the maximum of the last visit date or last contact date, including telephone follow-up where the subject is known to be alive.

As a primary analysis, a stratified one-sided log-rank test will be used to compare OS between the two treatment groups, with the one-sided significance level controlled at 0.025. The HR along with the 95% CI will be estimated using a stratified Cox model. For both the stratified log-rank test and the stratified Cox model, the strata will be those at randomization. A Kaplan-Meier plot for OS will be presented by treatment arm. Estimates and 95% CIs for the 25th percentile, median, and 75th percentile for OS will be presented by treatment arm (if estimable). Probabilities of survival at selected time points (3 months, 6 months, 9 months, and 12 months) may also be presented.

In addition, the following subgroup analyses will be performed:

- Subgroup analysis with unstratified log-rank test and unstratified Cox regression model. The HR (AG-120/placebo) with its 95% CI will be displayed for all subgroups graphically in a forest plot. The subgroups will include:
 - The actual number of prior line of therapies in advanced setting (1 vs. ≥ 2)
 - Gender (female vs. male)
 - Extent of disease at screening (locally advanced vs. metastatic)

- If subject had both locally advanced and metastatic, it would be considered as metastatic
- Intrahepatic vs. extrahepatic
 - Perihilar will be lumped into extrahepatic category
- ECOG at baseline (0 vs. ≥ 1)
- Regions (North America vs. Europe vs. Asia)

Per the protocol, placebo subjects are allowed to cross over to AG-120 upon the radiographic disease progression provided the eligibility criteria continue being met. To adjust for the crossover effect from placebo to AG-120 on OS, advanced modeling methods, such as rank preserving structural failure time (RPSFT) method, will be explored. More details of this method will be in the Appendix C: Overall Survival Analyses using Rank Preserving Structural Failure Time Model (RPSFT).

8.4. Multiple Comparisons/Multiplicity Adjustment

Of the secondary endpoints, OS and ORR are designated as key secondary efficacy endpoints. The primary and key secondary endpoints will be tested at an overall one-sided Type I error rate at 2.5% level based on the fixed sequence testing procedure at the time of primary analysis. These endpoints will be tested in the following order:

- PFS based on IRC
- OS
- ORR based on IRC

In addition, a hierarchical testing procedure will be adopted for OS analyses only if the primary efficacy endpoint PFS is statistically significant. Two analyses are planned for OS: 1) an interim analysis at the projected time of the final analysis for PFS (provided PFS is significant); 2) a final analysis for OS when 150 deaths are observed. Overall survival at the interim will be tested with the alpha being determined using the gamma spending function ($\gamma = -8$), and the overall Type I error rate will be controlled at the 1-sided 0.025 level. The log-rank test stratified by randomization stratification factor will be used to compare OS between the two treatment arms.

8.5. Time To Response (TTR)

Time to response is defined as the time (in months) from the randomization date to the date of first occurrence of confirmed/unconfirmed response per RECIST v1.1.

8.6. Duration of Response (DOR)

Among responders (subjects who have a best response of confirmed PR or CR), DOR in months will be calculated as the date of the first confirmed PR or CR to the date of the first PD or death, whichever is earlier. Duration of response = (Earliest Date of Death/Progression – Date of First Confirmed PR/CR + 1)/30.4375. The censoring rule will be the same as that for the PFS analysis

in [Table 1](#): Handling of Missing Response Assessment and Censoring for the Primary Analysis of PFS.

For both TTR and DOR, a listing will be provided for responders only.

8.7. Health-Related Quality of Life (HRQOL)

In general, descriptive statistics will be used to summarize the individual items and sub-scale scores of HRQOL (ie, QLQ-C30 and QLQ-BIL21), anchor-based questions (ie, PGI-S, PGI-C) and the EQ-5D-5L data at each scheduled assessment time point. Data listings will also be provided by each endpoint and visit for each subject.

Upon receipt of FDA's feedback in May 2017, anchor questions (PGI-S and PGI-C) were added and HRQOL assessment frequency was increased from every 6 weeks prior to 1 year/every 8 weeks thereafter (to tie with scan schedule) to every cycle (every 4 weeks). The changes were implemented in Protocol Amendment 3.0, Version 4, published in September 2017.

8.7.1. Brief Descriptions of Questionnaires

QLQ-C30 Questionnaire

The QLQ-C30 contains 30 items in total and each item is a 4-point or 7-point Likert scale. These 30 items can be categorized into a global health status/HRQOL scale, 5 functional scales, 3 symptom scales, and 6 single-item scales. Each of the multi-item scales includes a different set of items. No item occurs in more than one scale:

- 1 global health status scale (2 items)
- 5 functional scales: physical function (5 items), role function (2 items), emotional function (4 items), cognitive function (2 items), social function (2 items)
- 3 symptom scales: fatigue (3 items), nausea and vomiting (2 items), pain (2 items)
- 6 single-item assessments relating to dyspnea, insomnia, appetite loss, constipation, diarrhea, and financial difficulties.

QLQ-BIL21 Questionnaire

The QLQ-BIL21 contains 21 items in total and each item is a 4-point Likert scale. These 21 items can be grouped into 5 scales and 3 single items:

- 5 scales (18 items): eating symptoms (4 items), jaundice symptoms (3 items), tiredness (3 items), pain symptoms (4 items), anxiety symptoms (4 items)
- 3 single-item assessments related to treatment side-effects, difficulties with drainage bag/tubes, concerns regarding weight loss

PGI-S

The anchor-based questionnaire PGI-S contains the following 3 items:

- The severity of the physical functioning decline over the past week
- The severity of the appetite decrease over the past week
- The severity of the pain over the past week

The possible outcomes include:

- None
- Mild
- Moderate
- Severe
- Very Severe

PGI-C

The anchor-based questionnaire PGI-C contains the following 3 items:

- The overall change in the physical functioning since the start of taking the study medication
- The overall change in the appetite since the start of taking the study medication
- The overall change in the pain since the start of taking the study medication

The possible outcome includes:

- Very much better
- Moderately better
- A little better
- No change
- A little worse
- Moderately worse
- Very much worse

EQ-5D-5L Questionnaires

The EQ-5D-5L contains 5 dimensions (Mobility, Self-Care, Usual Activities, Pain/Discomfort, and Anxiety/Depression) as well as the EQ visual analogue scale (VAS). Five dimensions return categorical outcomes, and the VAS is a 0-100 number.

8.7.2. Statistical Analyses

8.7.2.1. QLQ-C30 and QLQ-BIL21 Analyses

Each scale will be transformed into a 0-100 score following EORTC guidelines:

- Estimate the average of the items that contribute to the scale; this is the *raw scale score*
- Use a linear transformation to standardize the *raw scale score*, so that it ranges from 0 to 100. $Scale\ score = (raw\ score - 1)/range * 100$. The only exception is Physical Function in QLQ-C30, where the scale score per EORTC QLQ-C30 manual is $[1 - (raw\ score - 1)/range] * 100$. Here, range is the difference between the possible

maximum and minimum response to each individual item. For instance, if the item is scored from 1 to 4, then $\text{range}=3$.

Transformed scores for each scale and the absolute change from baseline will be summarized by treatment and scheduled visit. A mixed-effect model with repeated measurements on the change from baseline across visits for key *scale scores* (such as pain, appetite loss, and physical function) over the course of before crossover period may be explored with baseline score, treatment, visit, treatment-by-visit as fixed effects, and subject as random effects.

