7. STATISTICAL ANALYSES

Unless specified otherwise, longitudinal data will be presented by “before crossover” and “after crossover” periods, defined as:

- **“After crossover”** contain data collected after placebo subjects crossed over to AG-120. COS will be the analysis set.
- **“Before crossover”** contain AG120 arm data and the Placebo arm data up till crossover.

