8.7.2.2. Anchor Based Approach to Find Clinically Meaningful Change

Estimation of meaningful change is achieved by computing the change scores for the EORTC-QLQ-C30 and EORTC-QLQ-BIL21 scores between baseline and follow-up associated with minimal improvement groups defined on PGI-C and change from baseline to post-baseline PGI-S ($\Delta\text{PGI-S}$) ratings as anchors. This approach will be taken for only before-crossover data. Minimally sufficient improvement is directly defined from the PGI-C by analyzing those subjects who report a minimal level of improvement on the anchors. Minimally sufficient improvement for the PGI-S is operationalized by taking the difference in PGI-S between baseline and follow-up and selecting participants with a one-point improvement. Average EORTC-QLQ-C30 and EORTC-QLQ-BIL21 scores will be computed for each of the anchor-based minimally sufficient improvement group definitions.

Relevant subscales of the EORTC-QLQ-C30 and EORTC-QLQ-BIL21 will be paired with their most-appropriate PGI-C/PGI-S rating (eg, the physical functioning PGI-C/S will be employed for the EORTC-QLQ-C30 physical function subscale). Similarly, the EORTC-QLQ-C30 appetite item and EORTC-QLQ-BIL21 eating symptoms subscale will be paired with the appetite PGI-C/S. Finally, the EORTC-QLQ-C30 and EORTC-QLQ-BIL21 pain subscales will each be paired with the PGI-C/S as anchors.

EORTC-QLQ-C30 and EORTC-QLQ-BIL21 change scores will be plotted as cumulative distribution functions (CDFs) for change. Cumulative distribution functions will be stratified on their respective anchor variables (PGI-C and $\Delta\text{PGI-S}$). In addition, after unblinding, the CDFs will be stratified by treatment-arm.

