8.8. Post Crossover

Upon the radiographic progression of disease, subjects will be unblinded. If it's determined that they received placebo, subjects will be allowed to cross over to AG-120, provided they continue to be eligible for the study. Data after crossover will be analyzed separately, but in a similar fashion as outlined above.

In particular, tumor assessments after crossover will be based on Investigator assessment. Tumor measurements will be re-baselined prior to the start of crossover. The corresponding endpoints include:

- PFS per Investigator assessment (PFS2)
- Objective response rate /best overall response per Investigator assessment. Note that SD<38 days of the first AG-120 dose date will be assigned as UNK.
- Time To Response and DOR per Investigator assessment

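### SAP 8.7.2.1 reverses one of the five QLQ-C30 functional scales and does not say why the other four differ; if their items are coded like the Physical Function items, those four scores come out as 100 − S

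*SAP*

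**What the plan says.** SAP 8.7.1 describes the QLQ-C30 and groups its function scales together: "5 functional scales: physical function (5 items), role function (2 items), emotional function (4 items), cognitive function (2 items), social function (2 items"). SAP 8.7.2.1 then sets the scoring: "Each scale will be transformed into a 0-100 score following EORTC guidelines". The raw score is the mean of the items, and the general formula is `(raw − 1)/range × 100`. One departure is allowed: "The only exception is Physical Function in QLQ-C30, where the scale score per EORTC QLQ-C30 manual is" `[1 − (raw − 1)/range] × 100`. Role, emotional, cognitive and social function therefore take the general formula, the same one as the symptom scales.

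On output, SAP 8.7.2.1 says: "Transformed scores for each scale and the absolute change from baseline will be summarized by treatment and scheduled visit". SAP 7 splits longitudinal output into before-crossover and after-crossover periods ("Unless specified otherwise, longitudinal data will be presented by" those two periods), and SAP 8.8 adds: "Data after crossover will be analyzed separately, but in a similar fashion as outlined above".

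The EORTC scoring manual is in the protocol's reference list (Section 14), but neither document reproduces it or states how the items are coded. SAP 8.7.2.3 says which end is better for EQ-5D-5L. SAP 8.7.2.1 does not do so for the QLQ scales.

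**The concern.** Five scales that the SAP places in one class are split one against four by a single sentence. The SAP cites the manual for the Physical Function formula but does not say why the other four functional scales should not follow it. The lead-in about EORTC guidelines gives a programmer grounds to query the sentence, but it does not override an explicit rule that allows one exception. A program written to the text would implement the split.

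Comparing HRQOL with placebo is a secondary objective (Protocol 6.2, SAP 2.2). If the four scales are coded in the same direction as Physical Function, improvement would be tabulated as worsening and the reverse. The magnitudes would look plausible and every score would lie within 0 to 100, so a range check would not reveal it.

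**Working it through.** **Inputs.**
- General formula, SAP 8.7.2.1: `S_gen = (r − 1)/range × 100`, where r is the mean of the items.
- Physical Function formula, same section: `S_PF = [1 − (r − 1)/range] × 100`.
- Scales and items, SAP 8.7.1: QLQ-C30 has 1 global scale (2 items), 5 functional (5, 2, 4, 2, 2), 3 symptom (3, 2, 2) and 6 single items. QLQ-BIL21 has 5 scales (4, 3, 3, 4, 4) and 3 single items.

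**Step 1: the plan's own figures.** For an item scored 1 to 4, range = 4 − 1 = 3, as the SAP states. Item counts: 2 + 15 + 7 + 6 = 30 for QLQ-C30 and 18 + 3 = 21 for QLQ-BIL21, both as stated.

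**Step 2: how the scores split.** QLQ-C30 yields 1 + 5 + 3 + 6 = 15 scores and QLQ-BIL21 yields 5 + 3 = 8, in total 23. As written, 22 take the general formula and 1 is reversed. Four of the five functional scales, with 2 + 4 + 2 + 2 = 10 of the 15 functional items, are on the opposite formula from Physical Function.

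**Step 3: the two formulas compared.** `S_gen + S_PF = 100` for every r and every range. With range 3:

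| r | S_gen | S_PF |
|---|---|---|
| 1 | 0 | 100 |
| 1.5 | 16.67 | 83.33 |
| 2 | 33.33 | 66.67 |
| 2.5 | 50 | 50 |
| 3 | 66.67 | 33.33 |
| 4 | 100 | 0 |

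Evaluating every attainable raw mean of the five functional scales with 1-to-4 items confirms the identity to rounding error.

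**Step 4: effect on change, arm difference and SD.** A raw mean that falls from 2.5 to 1.5 gives 16.67 − 50 = −33.3 under the general formula and 83.33 − 50 = +33.3 under the Physical Function formula. For arm means A and B, (100 − A) − (100 − B) = −(A − B), so the difference keeps its size and changes sign. The SD is unchanged.

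The smallest possible step, one category on one item of an n-item scale, is 100/(n × range). With range 3 that is 16.7 points for role, cognitive and social function (n = 2) and 8.3 for emotional function (n = 4). SAP 8.7.1 does not say which items are 7-point; with range 6 these steps halve.

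**Step 5: condition.** The formulas show that the five scales are treated differently. They do not show that the treatment is wrong. That depends on item coding, which the documents do not give. *Assumption:* the items of the four scales are coded like the Physical Function items. *Range:* from 0 scales reflected (none coded alike) to 4 (all coded alike).

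**Step 6: reach.** Counting score and change from baseline, in two periods:
- QLQ-C30: 15 × 2 × 2 = 60 by-visit summary sets.
- Both questionnaires: 23 × 2 × 2 = 92 sets.
- The four scales: 4 × 2 × 2 = 16 sets, which is 16/60 = 26.7% of the QLQ-C30 sets and 16/92 = 17.4% of all QLQ sets.

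Half of the 16 are after-crossover sets. SAP 6.4 and SAP 7 restrict that period to placebo subjects who switched to AG-120, so those 8 sets hold one group. They can show a reversed score or change but no arm difference. Only the 8 before-crossover sets compare arms.

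**The case against.** The strongest objection is that the deciding source is not in hand. Sharing a heading in SAP 8.7.1 does not prove that the five scales share item direction. If the other four ran the opposite way to Physical Function, the SAP's rule would be consistent and nothing would be reflected. This stands. A reader might infer that the SAP mis-scores four scales. The documents support only an unexplained asymmetry whose effect depends on coding they do not give.

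A reader might also infer that the reversed formula has no stated basis. It has one: the SAP attributes the Physical Function formula to the manual. What is missing is a reason for leaving the other four out.

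A third tempting reading is that arm differences are reversed throughout. They could be so only before crossover, because the after-crossover tables hold a single group.

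The consequence is also limited. HRQOL is outside the fixed testing sequence of PFS, OS and ORR (SAP 8.4). The named anchor pairings cover physical function, appetite or eating, and pain; for example, "the physical functioning PGI-C/S will be employed for the EORTC-QLQ-C30 physical function subscale". The mixed model is optional, and its named examples are pain, appetite loss and physical function. They are only examples, so the four scales are not ruled out, but none is named. Finally, "descriptive statistics will be used to summarize the individual items and sub-scale scores of HRQOL" and data are listed, so any reflected score can be recovered as 100 − S. All of this stands and sets the severity. Recovery, however, helps only someone who already knows that the direction is in doubt.

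**Conclusion.** The point holds in conditional form and is minor. Two things are certain from the text and the algebra: four of the five QLQ-C30 functional scales take the opposite formula from Physical Function, and the two formulas are exact reflections of each other. Whether any score is wrong cannot be determined from the documents. Under the assumption of like coding, up to 4 of 15 QLQ-C30 scores are reflected, with size and SD unchanged. What is at stake is misread descriptive tables for four scales of a secondary objective. The primary and key secondary endpoints, the named anchor pairings and the named mixed-model examples are not affected.

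**What to change.** Before database lock, reconcile the sentence in SAP 8.7.2.1 with the EORTC QLQ-C30 scoring manual that it invokes.

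- If the manual codes the items of the five functional scales alike, replace the sentence with: *For the five QLQ-C30 functional scales (physical, role, emotional, cognitive, social), scale score = [1 − (raw score − 1)/range] × 100; for all other scales, scale score = (raw score − 1)/range × 100.* That gives 5 reversed and 18 unreversed scores in place of 1 and 22. Correct the scoring program to match.
- If it does not, add one clause saying why Physical Function differs from the other four.

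In either case, state which end of each QLQ-C30 and QLQ-BIL21 scale is better, as SAP 8.7.2.3 already does for EQ-5D-5L. The cost is a sentence or two in the SAP and at most one program line, with no new data.

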9.4. Method of Assigning Subjects to Treatment

Subjects who meet all study eligibility criteria will be randomly assigned in a 2:1 ratio, stratified by number of prior systemic treatment regimens for advanced disease (1 or 2), to receive AG-120 orally QD or AG-120-matched placebo orally QD.

The randomization schedule will be generated by an independent statistical group. The randomization assignment will be implemented by an interactive web response system (IWRS).

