12.7. Efficacy Analyses

Response to treatment will be assessed by the site Investigators and by the IRC using RECIST v1.1 (see Section 10.7).

To control the overall Type I error rate at the 5% level, the fixed sequence testing procedure (Westfall and Krishen 2001) will be used to adjust for multiple statistical testing of the primary and selected secondary efficacy endpoints. These endpoints will be tested in the following order:

- PFS based on IRC
- OS
- ORR based on IRC

No adjustment to the α level will be made for the other analyses.

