12.8. Analyses of Health-Related Quality of Life and Health Economic Outcomes

12.8.1. Health-Related Quality of Life Analyses

The EORTC-QLQ-C30, EORTC-BIL21, PGI-C, and PGI-S questionnaires will be used to collect data on the subject's functioning, disease-related symptoms, HRQOL, and health status. If a subject is not able to speak any language that is covered by the EORTC-QLQ-C30, EORTC-QLQ-BIL21, PGI-C, or PGI-S, the data from those instruments will be missing throughout the duration of that subject's involvement in the study. The number and percentage of subjects with the entire questionnaire missing will be summarized by treatment. Details including the missing data handling will be specified in the SAP.

Descriptive statistics (eg, means and medians) will be used to summarize the individual items and sub-scale scores of HRQOL data as well as PGI-C and PGI-S scores at each scheduled assessment time point by treatment. Additionally, change from baseline in the domain scores at the time of each assessment will be summarized by treatment. A repeated measurements analysis model may be used to compare the two treatment groups with respect to changes in the HRQOL domain scores as well as the PGI-C and PGI-S scores longitudinally over time. In addition, anchor-based method will be used to analyze the key domains with the specific anchor questions (PGI-C and PGI-S).

Detailed analysis plan will be specified in the SAP.

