4. OVERALL STUDY DESIGN

This is a Phase 3, multicenter, randomized, double-blind, placebo-controlled efficacy and safety study of orally administered AG-120 in subjects with advanced cholangiocarcinoma (nonresectable or metastatic). Subjects, all personnel involved in the evaluation of subjects' response to treatment (eg, Investigators, study coordinators, study pharmacists), and designated Sponsor team members will be blinded to study treatment until documented disease progression.

Subjects are required to have a histologically consistent diagnosis of IDH1 gene-mutated cholangiocarcinoma that is not eligible for curative resection, transplantation, or ablative therapies. Subjects must have documented progression of disease and have received treatment with at least 1 but not more than 2 prior treatment regimens for advanced disease (nonresectable or metastatic). At least 1 of the prior regimens must have included gemcitabine or 5-FU. Systemic adjuvant chemotherapy will be considered a line of treatment if there is documented disease progression during or within 6 months of completing the therapy, with Sponsor approval.

A total of approximately 186 subjects will be randomized in a 2:1 ratio to the AG-120 and placebo arms, respectively, stratified by number of prior therapies (1 vs. 2). The primary analysis of PFS will occur once 131 PFS events have been determined by Investigator assessment. Overall survival will be analyzed twice, once at the time of PFS primary analysis and once at the occurrence of 150 OS events.

Subjects who meet all study eligibility criteria will be randomly assigned in a 2:1 ratio to receive AG-120 orally at a dose of 500 mg once daily (QD) or AG-120-matched oral placebo QD. Daily study treatment will begin on C1D1. Cycles are 28 days (+/-2 days) in duration and dosing is continuous. Study visits will be conducted every other week during Cycles 1-3 (Days 1 and 15), and Day 1 of each cycle thereafter. Radiographic assessment (computed tomography [CT] or magnetic resonance imaging [MRI]) for evaluation of disease response will be conducted every 6 weeks (± 5 days) for the first 8 assessments (ie, through week 48) and every 8 weeks (± 5 days) thereafter from C1D1, independent of dose delays and/or dose interruptions, and/or at any time when progression of disease is suspected.

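### The optional HRQOL mixed model states only a random subject effect and omits the randomisation stratum; its by-visit standard errors are miscalibrated if correlation with baseline decays

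*SAP*

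**What the plan says.** SAP 8.7.2.1 commits to descriptive summaries of the transformed scores and their change from baseline by treatment and visit. It then mentions "A mixed-effect model with repeated measurements on the change from baseline across visits" for key scales such as pain, appetite loss and physical function, restricted to data before crossover, as something that might be tried, "with baseline score, treatment, visit, treatment-by-visit as fixed effects, and subject as random effects". Nothing further is given: no covariance structure, estimation method, degrees of freedom or fallback.

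Protocol 12.8.1 is equally permissive ("A repeated measurements analysis model may be used to compare the two treatment groups") and leaves the detail to the SAP.

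Randomisation is stratified by one or two prior regimens (Protocol 9.4; SAP 4). That stratum enters the main PFS, OS and ORR tests (SAP 8.1.1, 8.3, 8.2), although ORR falls back to an unstratified Fisher test when responders are few. It does not enter the HRQOL model.

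The tested sequence in Protocol 12.7 and SAP 8.4 is IRC PFS, OS, IRC ORR. For everything else, Protocol 12.7 says: "No adjustment to the α level will be made for the other analyses".

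**The concern.** A single random subject effect with independent residuals implies compound symmetry: one variance for all visits and one correlation for every pair of visits. Repeated symptom scores often behave otherwise, with neighbouring visits more alike than distant ones. The model adjusts for baseline score, so what matters is the variance left after that adjustment, and this grows as correlation with baseline fades. A model that averages over visits then overstates uncertainty early and understates it late.

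HRQOL against placebo is a secondary objective, and the questionnaires are given every cycle, so by-visit differences are likely to be read. Late visits have the fewest subjects and would carry the intervals that are too narrow. The missing stratum is a separate matter with a different effect.

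**Working it through.** The plan gives no HRQOL standard deviation, correlation, effect size or power, so there is no figure to reproduce. The check asks how far the model-based standard error can differ from the true one.

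**Inputs from the documents.** 124 vs 62 subjects (Protocol 8.1); assessments every 4 weeks (SAP 8.7); exponential PFS with medians of 6 and 3 months (SAP 5), borrowed here as the attrition rate.

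**Assumptions.** Six post-baseline visits (C2 to C7), ignorable dropout, raw SD 20, and correlation patterns shown as a range.

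**1. Subjects remaining.** At visit k, t = 28k/30.4375 months.
- Visit 1 (t = 0.92): 124 × 0.5^(0.92/6) ≈ 112; 62 × 0.5^(0.92/3) ≈ 50.
- Visit 6 (t = 5.52): about 66 and 17.

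**2. Residual variance after baseline adjustment.** It equals SD² × (1 − ρ_k²), where ρ_k is the correlation of visit k with baseline. With 15% noise and decay of 0.8 per visit, ρ_k = 0.85 × 0.8^k:
- Visit 1: ρ = 0.68, residual SD = 20 × √(1 − 0.462) = 14.7.
- Visit 6: ρ = 0.223, residual SD = 20 × √(1 − 0.050) = 19.5.

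So decay alone makes the residual SD rise, even though the raw SD is constant.

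**3. Standard-error ratio.** Let V be the true covariance and W the compound-symmetry matrix that best fits it by likelihood. Within each arm, summing over dropout patterns, B = Σ n W⁻¹ and M = Σ n W⁻¹ V W⁻¹. The model-based variance is the diagonal of B⁻¹ and the true variance is the diagonal of B⁻¹ M B⁻¹. Adding the arms and taking the root of the quotient gives model SE / true SE:

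| Assumed correlation, constant raw SD | C2 | C7 |
|---|---|---|
| Stable subject level plus noise, no decay | 1.00 | 1.00 |
| Partly stable (stable/decaying/noise 60/10/30, 50/20/30, 50/35/15%) | 1.03 to 1.15 | 0.96 to 0.87 |
| Decay 0.8 to 0.9, 30% noise | 1.10 to 1.11 | 0.89 to 0.90 |
| Decay 0.95, 15% noise | 1.15 | 0.85 |
| Decay 0.8, 15% noise | 1.19 | 0.85 |
| Decay 0.9, 15% noise | 1.19 | 0.83 |

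These figures adjust for baseline separately at each visit. A single baseline slope, as the SAP lists it, gives a similar pattern.

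**4. What the extreme case means for a nominal two-sided 5% test.** The rejection rate under no effect is 2 × [1 − Φ(1.96 × ratio)].
- Ratio 1.19: 1.96 × 1.19 = 2.33, about 2%.
- Ratio 0.83: 1.96 × 0.83 = 1.63, about 10%.

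**5. When the direction changes.** If the raw SD falls from 22 to 18 while correlation decays at 0.8 to 0.9 with 15% noise, the ratio still runs from 1.10–1.11 down to 0.91–0.93. If the SD of the modelled outcome itself falls from 22 to 18 with equal correlation of 0.6, it reverses: 0.93 at the first visit and 1.13 at the sixth.

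**6. Omitted stratum.** Stratified allocation balances the stratum between arms, but a model without it leaves that variance in the residual. The standard error is inflated by 1/√(1 − R²): 1.005 at R² = 1%, 1.026 at 5%, 1.054 at 10%. Simulation with stratified allocation gave ratios of 1.00 to 1.03 for stratum differences of 5 and 10 points, with no early or late trend.

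**The case against.** The strongest reply is that the SAP promises little here. The model is optional in both documents, the committed HRQOL analysis is descriptive, and HRQOL lies outside the tested sequence. That stands: no confirmatory error rate is touched.

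Second, the reference to repeated measurements leaves room for a within-subject residual structure, so a reader who infers that the SAP commits to compound symmetry goes further than the sentence does. That also stands, but two programmers could then fit different models to the same text, which is itself a reason to specify it.

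Third, a reader might infer that the standard errors simply are wrong, too wide early and too narrow late. The documents do not support that as fact. With a stable subject level plus noise the random intercept is exactly right, and if the residual SD falls over visits the error can run the other way. The direction is conditional on decay and the size is unknown.

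Fourth, the remedy is not proven at this sample size. Calibration under the true covariance is good by construction. An unstructured matrix over six visits has 6 × 7 / 2 = 21 parameters to estimate, with about 17 placebo subjects at the sixth visit under the assumed attrition. This is why the fix limits the visits and names a fallback.

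**Conclusion.** The point holds as a minor specification gap. As written, the model's only stated within-subject structure is a random subject effect, and the randomisation stratum is missing. If correlation with baseline decays at roughly constant raw SD, by-visit standard errors are too large first and too small later, with ratios between 1.00 throughout and about 1.19 at C2 falling to 0.83 at C7. That range rests on assumed HRQOL variances and correlations, on PFS medians standing in for questionnaire attrition, and on ignorable dropout.

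The stratum omission should not be read as the cause of the early/late pattern: its effect is a small, uniform overstatement of about 0.5% to 2.6% if the stratum explains 1% to 5% of the variance. The PFS, OS and ORR conclusions are unaffected.

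**What to change.** In SAP 8.7.2.1, specify the model, should it be run, as follows:
- Fixed effects: baseline score, baseline-by-visit, treatment, visit, treatment-by-visit and randomisation stratum (1 vs 2 prior lines). Baseline-by-visit lets the baseline slope change as correlation fades.
- Within-subject covariance: unstructured across the analysis visits, in place of the random intercept, fitted by REML with Kenward-Roger degrees of freedom.
- Analysis visits: only those with enough subjects in each arm, using a minimum number stated in advance.
- Fallback if the fit does not converge: an ordered list, such as heterogeneous Toeplitz next.

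The cost is a few lines of SAP text and a changed model statement in the program. No new data are needed.
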